This statistical analysis plan covers the interim and final analyses of the Oncopain study T2001-01. As specified in the study protocol, the interim analysis will be executed as soon as 60 patients have completed the study.

The primary objective of the complete study consists in finding predictive factors of pain management and analgesic treatment efficacy in patients suffering from CIBP (cancer-induced bone pain). The analyses necessary to achieve this objective are very complex to conduct, due to the complexity of the data available. Secondary objectives describe intermediate milestones which will be reached during these analyses.

An interim analysis is also planned for the validation of sample size and necessary items among the personality tests.

All statistical analyses related to the study will be the responsibility of DNAlytics or designee. They will be conducted on the full analysis set. This set includes all data from patients who have been screened and who completed the study (no drop-outs). No safety analyses will be conducted during the interim study. The safety analyses on the complete database will be performed by the sponsor and reported in the Clinical Study Report. Additional exploratory analyses of the data will be conducted as deemed appropriate.

All hypothesis tests will be conducted at a two-sided alpha level of 0.05, unless otherwise stated.

Name	Company	Role
[name]	DNAlytics	Study design, analysis implementation, reporting
[name]	DNAlytics	Study design, analysis review, reporting
[name]	DNAlytics	Study design, analysis and report review
[name]	Tools4Patient	Study design. As study sponsor representative, monitors data analysis progress.

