4.2 Study Participant Characteristics

The following variables will be recorded and may be used as quantitative or classification variables:

- Patient characteristics, measured at V1:
 - Study center
 - Patient's sociodemographic characteristics: age, sex and other demographic characteristics
 - Recent analgesic treatment history
 - Personality questionnaires, at facet- and domain-level: Multidimensional Health Locus of Control Scale (MHLCS, with domains I, C and P), Hospital Anxiety and Depression Scale (HADS), Revised Life Orientation Test (LOT-R) and Expectation.
 - Pain evaluation questionnaires: Douleur Neuropathique en 4 questions (DN4), Neuropathic Pain Symptom Inventory (NPSI), and Pain Catastrophizing Scale (PCS)
- Pain and quality of life assessment, measured at V1 and V2:
 - Brief Pain Inventory (BPI)
 - Quality of Life questionnaire in 30 questions (QLQ-C30), IGAC, PGAC
 - Clinical Pain Assessment (CPA): Static Allodynia (SA), Dynamic Mechanical Allodynia (DMA), Mechanical Pain Threshold (MPT), Thermal Pain Sensitivity (TPS)
- Follow-up from the daily diary and intermediate visit:
 - Daily Average and Worst Pain Score (APS and WPS),
 - Daily analgesic therapy (including rescue medication): number of distinct drugs intaken, number of distinct drug categories intaken
 - Intake of rescue analgesic treatment if any,

Note that the description of analgesic therapy hereabove requires the grouping of drugs into a small number of classes which will be described in the Statistical Analysis Report.

The collection of the values of all these variables and variables derived from them for a single patient is referred to as *the patient-vector* below in the text.

5 Description of the Analyses

The final statistical analysis covers four aspects (Ax) detailed in the following sections:

- A1: Descriptive statistics at baseline, covering secondary objectives number 1 and 2.
- A2: Evolution of daily pain and treatments, covering secondary objective number 3.
- A3: Prediction of treatment efficacy, covering the primary objective

In addition, the interim statistical analysis will cover the following two aspects, corresponding to the interim objectives:

- I1: Sample size computation for the prediction of treatment efficacy.
- I2: Relation between psychological traits and pain evolution

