5.3 A3: Prediction of treatment efficacy

A predictive model will be tuned based on the characteristics at V1 in order to predict the efficacy of each treatment on the patient. One model will be built for each treatment t, with the following design:

- Scope: patients having received treatment t on some but not all days
- Response (target): Per-patient treatment effect, as measured by the average difference of daily APS between the days with and without treatment t
- Predictors: patient characteristics at baseline

The performances of these pre-treatment models will be evaluated inside a resampling procedure. This procedure repeatedly samples 80% data to learn a predictive model whose predictive performances are assessed on the 20% remaining unseen data. In total, 200 train-test splits are performed for each treatment. The predictive model in use will be a ridge regression, as implemented by glmnet::cv.glmnet in R, with parameter alpha=0.

Table (tab-pred-perf) will report the average predictive performance on the test sets for each treatment, in terms of relevant statistics.

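### A3, the only analysis for the primary objective, reports average held-out performance with no mean-only benchmark, test or correction across treatments, so under some metrics chance can be read as prediction

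*SAP*

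**What the plan says.** The list that opens SAP section 5 assigns the objectives. A1 and A2 serve the secondary ones, and the primary one falls to A3 alone: "A3: Prediction of treatment efficacy, covering the primary objective".

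SAP 5.3 describes A3. "One model will be built for each treatment t", in this population: "Scope: patients having received treatment t on some but not all days". The response is each patient's mean APS difference between days with and without the treatment, and the predictors are baseline characteristics. The model is a ridge regression scored by resampling: "This procedure repeatedly samples 80% data to learn a predictive model", with the other 20% used for testing. "In total, 200 train-test splits are performed for each treatment". The output is then defined: "Table (tab-pred-perf) will report the average predictive performance on the test sets for each treatment, in terms of relevant statistics".

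SAP 5.3 contains no metric, comparator, interval, test, success criterion or correction across treatments. The introduction says "All hypothesis tests will be conducted at a two-sided alpha level of 0.05, unless otherwise stated", but A3 has no hypothesis test to which this could apply. Other sections are more specific: Spearman and Fisher tests with a multiplicity correction in A1.4, Wilcoxon tests in A2.1 and A2.2, and BH correction in A2.3 and I2.

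The number of models is also open. SAP 4.2 says that the description of therapy "requires the grouping of drugs into a small number of classes which will be described in the Statistical Analysis Report", and SAP 5.3 does not say whether a treatment means a drug or a class.

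**The concern.** The primary question is whether baseline characteristics predict how well a treatment works. A performance figure answers it only if the reader knows what the same procedure yields when nothing is predictable. A3 gives no such reference. Its 200 splits reuse one set of patients, so the averaging removes the noise of the split and keeps the noise from which patients were sampled. With one row per treatment, the eye goes to the best row, and nothing in the plan allows for that selection.

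The interim is affected too. I1 (SAP 5.4.1) extrapolates the same average performance to 140 patients in order to confirm or revise the sample size, again without a no-information line.

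**Working it through.** **Inputs from the documents.** 80/20 splits, 200 per treatment, ridge through cv.glmnet (SAP 5.3); about 140 completers from up to 180 enrolled (protocol 4.2.1); 60 completers at the interim (SAP introduction). Protocol 4.2.1 rests the sample size on published studies, and no error rate or target performance is given for A3. There is therefore no figure of the plan's own to reproduce.

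**Assumptions, where the documents are silent.** Patients per treatment n = 12 to 90; number of treatments K = 4, 5, 10 or 20; 15 to 40 independent predictors, none related to the response; treatments independent of each other.

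**Step 1: size of each test set.** 0.2 × 20 = 4 patients, 0.2 × 45 = 9, 0.2 × 90 = 18.

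**Step 2: null spread of the averaged test correlation.** Simulation with 30 predictors, leave-one-out penalty choice, 60 splits and 150 data sets per size:

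| n | SD | mean of best of 10 | mean of best of 4 |
|---|---|---|---|
| 20 | 0.27 | 0.37 | 0.24 |
| 45 | 0.18 | 0.28 | 0.19 |
| 90 | 0.14 | 0.22 | 0.15 |

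The Monte Carlo error of the first SD is about 0.27/√(2 × 149) = 0.016.

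**Step 3: a version closer to the SAP.** 40 predictors, 10-fold inner cross-validation on a glmnet-like penalty grid (minimum-error penalty), 200 splits, 400 data sets per size. The chance that at least one of K treatments exceeds r = 0.3 is 1 − (1 − q)^K, where q is the chance for one treatment:

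| n | mean r | SD | 95th percentile | q | K = 5 | K = 10 |
|---|---|---|---|---|---|---|
| 12 | 0.01 | 0.30 | 0.49 | 18.8% | 65% | 87% |
| 20 | 0.00 | 0.27 | 0.42 | 14.7% | 55% | 80% |
| 30 | 0.00 | 0.23 | 0.37 | 9.8% | 40% | 64% |

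For example, 1 − 0.853^10 = 0.80. The mean near zero shows that there is no upward bias. The SD at n = 20 matches step 2 although the number of splits is 200 instead of 60, so more splits do not remove the spread. With 15 predictors at n = 20, q is 13.6%. The 0.3 mark is illustrative; no document sets a threshold.

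**Step 4: dependence on the metric.**
- *RMSE.* In the step 3 runs, including those with 15 predictors, the null average is 0.94 to 1.05 outcome SDs, with 5th to 95th percentiles spanning 0.62 to 1.35. An RMSE without the mean-only RMSE beside it cannot be interpreted.
- *R2 averaged over splits.* Above 0 in none of the step 2 null data sets. A separate run (30 predictors, 10-fold, 30 splits, 100 data sets each at n = 20, 45 and 90) also gave none above 0 under either penalty rule, with means from −1.25 to −0.09. With leave-one-out tuning, the means were about −1.9 at n = 20 and −0.4 at n = 45.
- *R2 pooled over test predictions (Q2).* Centred close to or below 0, but its sign alone is not a test. At n = 20 with 40 predictors it exceeded 0 in 23.0% of null data sets with the minimum-error penalty and in 48.5% with the one-standard-error penalty. With 15 predictors the figures were 4.8% and 5.2%.

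**Step 5: tests without correction.** One test per treatment at 0.05 gives at least one false positive with probability 1 − 0.95^K: 22.6% for K = 5, 40.1% for K = 10, 64.2% for K = 20.

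**The case against.** The strongest reply is that A3 already scores unseen data. That is right as far as bias goes: null performance centres on no prediction. A reader might infer that the best row is bound to look predictive when nothing is. The documents do not support that, because the metric is unnamed, and under an averaged per-split R2 no null data set scored above zero.

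Second, the group sizes and number of treatments are assumed. If a treatment in A3 is one of the small number of classes mentioned in SAP 4.2, there may be few rows with many patients each. At n = 90 a separate run gave SD 0.13, no null correlation above 0.3, and a best of 4 averaging 0.12. This stands as a limit on size: the spread shrinks but does not vanish.

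Third, SAP 6.1 refers to an attached table template that was not available for this review and may name the statistics. It could settle the metric, but SAP 5.3 would still contain no test or correction.

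Fourth, A2.3 tests baseline factors against the APS trend with BH correction, and SAP 2.5 lists that trend as an efficacy endpoint. Factor-level inference is therefore not absent, but the SAP maps A2 to secondary objective 3.

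Fifth, the work is exploratory in tone. Protocol 10.1.1.2 (P3) states only aims, and protocol 4.2.1 disclaims prior hypothesis tests. That disclaimer concerns how the sample size was set, and P3 leaves the procedures to the SAP. A strict 0.05 rule is partly a matter of preference; a no-information reference is not.

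**Conclusion.** The omission is plain in SAP 5.3, and it affects the only analysis mapped to the primary objective. Chance performance can be read as prediction if the reported statistic is a correlation, or an RMSE without its mean-only counterpart. A per-split R2 averaged over splits does not carry that risk, though it is strongly negative under the null in small groups and so is a poor summary there.

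Under the null with 30 predictors, the averaged correlation has SD about 0.27, 0.18 and 0.14 at 20, 45 and 90 patients per treatment. The best of 10 averages about 0.37, 0.28 and 0.22, and the best of 4 about 0.24, 0.19 and 0.15. These sizes rest on assumed numbers of patients, treatments and predictors. Treatments will share patients, so independence between them is an approximation.

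A reader might go further and say that the table can support no conclusion in either direction. The documents do not support that: a metric with a built-in zero, which the SAP neither names nor excludes, would carry some information. The supported conclusion is that the plan does not ensure that prediction can be told from chance.

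**What to change.** In SAP 5.3:

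1. List the treatments or drug classes to be modelled, and a minimum number of in-scope patients for each, before A3 is run. The correction in item 4 needs a fixed family, and SAP 4.2 currently leaves the grouping to the report.
2. Name one primary statistic per treatment, pooled over all test predictions: Q2 = 1 − (squared error of the model)/(squared error of the training-set mean). State the penalty rule.
3. Repeat the whole resampling procedure, tuning included, with the response permuted across that treatment's patients, and report the permutation p-value. With 1,000 permutations the smallest attainable value is 1/1001, about 0.001, below the strictest BH step for 10 treatments (0.05/10 = 0.005). If fewer splits are used per permutation, compute the observed statistic for the p-value with the same number.
4. Apply BH across the listed treatments, and call a treatment's efficacy predictable only where Q2 > 0 and the corrected p-value is below 0.05. Step 4 of the working shows why Q2 > 0 alone is not enough. BH controls the false discovery rate; Holm would be the choice if familywise control were wanted.

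In SAP 5.4.1 (I1), show the same no-information reference on the learning curve.

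No new data are needed. The cost is SAP wording and computing time, and some encouraging averages will be reported as no better than chance.

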10.1.1.2. General Statistical Procedures

The statistical analyses will be divided into four main parts (P1 to P4): descriptive, univariate, multivariate and exploratory. The descriptive part intends to describe the data by generating a set of statistical summaries of each patient-vector entry. The univariate analysis will investigate the link between each patient-vector entry and the treatment response (as described by the pain evolution). All the statistical procedures will further be described in a dedicated SAP.

P1 - Data Description

P11: Data pre-processing and summary.

Classical statistical information will be computed for each input feature (mean, median, standard deviation). A log-transform will be applied to some features, when appropriate.

P12: Missing values management.

The number of missing values will be reported for each feature. In subsequent analyses, value imputation might be performed if needed. Such cases will be documented.

P13: Outlier detection.

Population outliers will be detected through a Principal Component Analysis (PCA) visualization. Outliers might be removed for at least parts of the further analyses. Such cases will be documented.

P2 - Univariate Analysis

P21: Features Impact Assessment.

The correlation between each feature and the treatment response in terms of target feature will be assessed.

For each test performed in P2, if a non-conclusive p-value is obtained and when possible, an estimation of the required sample size will be performed based on the study data.

P3 - Multivariate Analysis

The aims of the multivariate analysis are i) to explore links between features (including all input and target features), ii) to predict target features based on input features, iii) to identify most important input features for this predictive task.

P4 - Exploratory Analysis

P41 - New populations identification.

We identify subgroups of patients with intra-group similar pain evolution curves, and inter-group different pain evolution curves. We define new “class labels” accordingly. If coherent profiles are found, we might consider applying a modeling procedure similar to P3.

P42 – Genetic data exploitation.

In case the genetic material from patients is used, similar experiments as those described above might be performed to discover links between genetic traits (snips for example) and pain evolution or pain treatments efficacy.

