2.1 Primary Objective (for the whole study)

To define predictive factors of pain management/treatments efficacy in cancer patients with bone metastases suffering from pain (or cancer-induced bone pain (CIBP)), based on individual patient disease, therapy history, personality traits and expectation.

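### A3, the only analysis assigned to the primary objective, pre-specifies no output or rule for identifying predictive factors and reports only ridge test-set performance

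*SAP*

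**What the plan says.** SAP section 2.1 gives the primary objective: "To define predictive factors of pain management/treatments efficacy in cancer patients with bone metastases suffering from pain". The list that opens SAP section 5 maps analyses to objectives. The baseline work is tied to the first two secondary objectives ("A1: Descriptive statistics at baseline, covering secondary objectives number 1 and 2"). The study of pain and therapy over time is tied to the third ("A2: Evolution of daily pain and treatments, covering secondary objective number 3"). Only the prediction models are tied to the primary one: "A3: Prediction of treatment efficacy, covering the primary objective". No other analysis is mapped to the primary objective.

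SAP section 5.3 sets out A3. For each treatment, the response is a patient's mean difference in daily Average Pain Score (APS) between days on and days off that treatment, and the predictors are baseline characteristics. "The predictive model in use will be a ridge regression, as implemented by glmnet::cv.glmnet in R, with parameter alpha=0". Each split trains on 80% of the data and tests on 20%: "In total, 200 train-test splits are performed for each treatment". The one named output is Table tab-pred-perf, which "will report the average predictive performance on the test sets for each treatment, in terms of relevant statistics". In the figure list (SAP section 6.2), the only prediction figure is Figure 7, a learning curve of performance.

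Protocol section 10.1.1.2 gives the multivariate part (P3) three aims. The second is to predict the targets; the third is "iii) to identify most important input features for this predictive task".

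**The concern.** The protocol treats prediction and identification as separate aims. A3 carries over the first and leaves out the second, yet it is the analysis meant to answer an objective about factors. A good test-set result would show that baseline data carry information about response to a treatment. It would not say which data.

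If coefficients or rankings are then produced after the results are seen, under the SAP's general allowance for further exploratory analyses, the answer to the primary objective becomes post hoc, with no rule fixed for what counts as a factor.

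**Working it through.** The plan states no figure to reproduce. Protocol section 4.2.1 says that no hypothesis test or precision target was used to set the sample size. The check is mainly a comparison of texts, followed by two calculations.

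**1. What each analysis delivers**

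| Analysis | Mapped objective | Outcome | Per-variable result? |
|---|---|---|---|
| A1.4 | Secondary 1 and 2 | Baseline pain | Yes, but not treatment efficacy |
| A2.3 | Secondary 3 | Per-patient APS slope | Yes: univariate, BH-corrected |
| A3 | Primary | Per-treatment on/off difference in APS | None planned |

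**2. Was the identification aim withdrawn?** SAP section 1.2 lists two changes from the protocol: an added secondary endpoint and added secondary objectives. Section 1.3 describes the primary objective as unmodified. Neither mentions P3's third aim.

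**3. Does fitting ridge name factors by itself?** No. Here alpha = 0 is the glmnet mixing parameter, which gives a pure squared (L2) penalty. It shrinks coefficients without setting them to zero, so no variable is selected.

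**4. Can average performance stand in for identification?** An illustrative simulation of the A3 scheme was run. Assumptions not in the documents: 30 independent predictors; three true factors with joint R² of 0.30, or none; 40 data sets with 20 splits each. Mean test R² (standard error):

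| n | True factors 1–3 | True factors 11–13 | No true factor |
|---|---|---|---|
| 60 | 0.017 (0.012) | 0.019 (0.016) | −0.021 (0.006) |
| 140 | 0.113 (0.010) | 0.142 (0.011) | −0.008 (0.002) |

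No coefficient was exactly zero in any fit. The predictors are exchangeable by construction, so the two sets have the same expected performance and the gap at n = 140 is simulation noise. A performance table looks the same whichever variables carry the signal.

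**5. Would coefficient spread across the splits be enough to declare factors?** This matters for the remedy. Suppose an estimate behaves like a mean with variance σ²/n. Subsamples of size m = 0.8n, drawn without replacement from the same patients, vary around the full-sample estimate with variance

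σ²(1/m − 1/n) = (σ²/n)(1/0.8 − 1) = 0.25 σ²/n,

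so the spread is 0.5 of the sampling standard error. A 2.5–97.5 percentile range then has half-width 1.96 × 0.5 = 0.98 standard errors. For a pure-noise feature, the chance that it excludes zero is P(|Z| > 0.98) ≈ 0.33. With 30 noise features, 30 × 0.327 ≈ 9.8 would appear stable. A noise-only simulation (30 independent predictors, cross-validated ridge, 200 splits, 30 data sets per n) gave 8.5, 9.3 and 10.2 of 30 at n = 30, 60 and 140, and every data set had at least one. The range describes stability; it is not a confidence interval.

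**The case against.** The strongest counter-argument is A2.3. It tests every visit 1 characteristic against the APS slope with BH correction. SAP section 2.5 lists that slope under individual treatment efficacy, and section 1.3 calls the secondary objectives milestones towards the primary one. The objective also speaks of pain management as well as treatments, so it is not confined to single drugs. A reader might infer that the study as planned cannot name one predictive factor of efficacy. The documents do not support that: A2.3 can name baseline variables associated with an endpoint that the SAP itself labels efficacy.

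What remains is narrower. A2.3 is univariate, pools all treatments, sits under secondary objective 3, and uses neither the primary endpoint nor A3's response. A variable correlated with the slope may reflect the course of pain without predicting response to any treatment.

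Three further points are fair.

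- Ridge coefficients exist and could be reported. The defect is that no report or rule is planned; the choice of ridge is not at fault.
- A3's on/off contrast is not the primary endpoint (change from baseline in weekly mean APS). A factor table for A3 therefore does not, by itself, give factors for that endpoint.
- The table-template file cited in SAP section 6.1 is not among the documents, so its columns cannot be checked. The SAP text describes tab-pred-perf as performance only.

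**Conclusion.** The concern holds for A3. Its one named table contains no per-feature result, so the analysis mapped to the primary objective names zero factors for every treatment, and a protocol aim has been dropped without being declared. This follows from the text and does not depend on the simulations, which only show why performance, or unadjusted split ranges, cannot fill the gap. It assumes that the unseen table templates add no factor output to A3.

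It does not extend to the whole SAP, because A2.3 is a genuine per-variable screen on a secondary efficacy endpoint. The gap should be closed before database lock, by which time protocol section 10.1.1 requires the SAP to be final.

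**What to change.** Keep ridge and add the following to SAP section 5.3.

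- **One table per treatment.** For each feature, give the mean standardised coefficient, sign consistency and spread across the 200 splits (labelled as stability, not as a confidence interval), and the loss of test-set performance when that feature is permuted.
- **A reference.** Rerun A3 with the response shuffled across patients and compare each measure with its shuffled distribution, with multiplicity control across features. Shuffling represents the case of no factor at all, so calibration for one feature is approximate when others carry signal; say so in the SAP.
- **A gate.** Name factors only for treatments whose test performance exceeds the shuffled reference.
- **A named metric.** Replace the unspecified performance statistics with one stated measure. The interim learning curve (SAP section 5.4.1) relies on the same measure.
- **Grouping.** Facet and domain scores of one questionnaire are both predictors (SAP section 4.2), and ridge shares weight between them. Permute and rank them as a group.

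If identification is instead meant to be dropped, SAP section 1.2 should record that and the primary objective should be reworded.

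Cost: no new data and no change of penalty. With B shuffles, the training runs per treatment rise from 200 to 200 × (B + 1); permuting features needs no refitting. The report gains one table per treatment. The number of treatments is not given, because the drug classes are left to the Statistical Analysis Report.

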5.4.1 I1: Sample size computation for the prediction of treatment efficacy

For computing the necessary sample size, a *learning curve* will be evaluated for the analysis in A3. This analysis will first be run on all patients available in the interim database extract, and the average per-treatment performance will be computed. Then a random sample of 90% of the patients will be drawn and the same analysis will be repeated. And similarly with decreasing sample size.

This will lead to a "learning curve" showing the variation of predictive performance wrt to sample size and shown in Figure (7). An extrapolation of the curve will be performed in order to estimate the expected performance obtained in the final analysis using all 140 samples. A confirmation of infirmation of the number of patients to be included in the study will be made based on this estimation

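### Averaging per-split scores in A3 biases R² downward when test sets are small, and SAP 5.3 leaves open whether R² is used: name the statistic and pool the errors before scoring

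*SAP*

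**What the plan says.** SAP section 5 assigns the primary objective to A3 alone. Section 5.3 builds one model per treatment, a "ridge regression, as implemented by glmnet::cv.glmnet in R, with parameter alpha=0". Each model is restricted as follows: "Scope: patients having received treatment t on some but not all days". The outcome is given as "Response (target): Per-patient treatment effect, as measured by the average difference of daily APS between the days with and without treatment t", so each patient contributes one continuous value.

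On performance, 5.3 states: "This procedure repeatedly samples 80% data to learn a predictive model whose predictive performances are assessed on the 20% remaining unseen data". It adds: "In total, 200 train-test splits are performed for each treatment". Table tab-pred-perf "will report the average predictive performance on the test sets for each treatment, in terms of relevant statistics". The natural reading is that each test set is scored and the scores are then averaged. The section gives no statistic, no baseline for an R², no pooling rule and no minimum number of patients per treatment. SAP 6.1 points to a table template file that is not among the documents available here.

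I1 (SAP 5.4.1) reuses A3: "This analysis will first be run on all patients available in the interim database extract, and the average per-treatment performance will be computed". The analysis is then repeated on a 90% sample and on smaller ones, the curve is extrapolated to 140, and the result informs the decision on patient numbers. Figure 7 puts training-set size on the horizontal axis. The test set shrinks along with it and is not shown. Protocol 4.2.3 lets the interim either confirm the planned size or reduce it.

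**The concern.** R² about the test-set mean is a ratio whose denominator is the variation among the few patients in that test set. With few patients the denominator is sometimes very small, the ratio is strongly skewed, and the average of many such ratios is not the R² the model would achieve on a large new sample. This is bias rather than Monte Carlo noise, so running more than 200 splits does not remove it.

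Three things are at stake. The per-treatment results would not be comparable across treatments with different numbers of eligible patients. A weak but real signal could be reported as worse than no model. And in I1, where the test set shrinks with each subset, growth in test-set size would be read as learning.

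**Working it through.** **Inputs.** From the SAP: 80/20 splits, 200 per treatment, ridge with alpha=0, one value per patient, 60 completers at the interim, 140 as the extrapolation target. Not in the documents, and therefore assumed: the number eligible per treatment, the number of predictors, the signal strength and the rule for picking the ridge penalty. The plan states no performance figure to reproduce. Protocol 4.2.1 supports 140 by the size of similar studies, not by a calculation.

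**Test-set size**, m = 0.2 × n_t:
- Every completer eligible: 0.2 × 60 = 12 and 0.2 × 140 = 28.
- 10-50% eligible (assumed): n_t = 6-30 gives m of about 1-6 at the interim; n_t = 14-70 gives about 3-14 at the end.

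**No signal, predicting the training mean.** The squared error is SST + m × (test mean - training mean)². For normal outcomes the difference in means has variance σ²(1/m + 1/n_tr) and is independent of SST, and E[σ²/SST] = 1/(m-3). Hence E[R²] = -(1 + m/n_tr)/(m-3). At 80/20, m/n_tr = 0.25, giving -1.25/(m-3). The real cost of using the training mean is only -1/n_tr.

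| n_t | m | n_tr | -1.25/(m-3) | -1/n_tr |
|---|---|---|---|---|
| 20 | 4 | 16 | -1.25 | -0.06 |
| 30 | 6 | 24 | -0.42 | -0.04 |
| 40 | 8 | 32 | -0.25 | -0.03 |
| 60 | 12 | 48 | -0.14 | -0.02 |
| 140 | 28 | 112 | -0.05 | -0.01 |

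At m = 2 or 3 there is no finite mean; at m = 1 the score is undefined.

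**A predictor with known true R² = q.** E[R²] = 1 - [(1-q)² + q(1-q)(m-1)/(m-3) + (1-q)/(m-3)]. With q = 0.20:
- m = 6: 1 - (0.640 + 0.267 + 0.267) = -0.17
- m = 12: 1 - (0.640 + 0.196 + 0.089) = 0.08
- m = 28: 1 - (0.640 + 0.173 + 0.032) = 0.155

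**Ridge simulation.** Assumed: 40 correlated predictors, penalty by 10-fold cross-validation (lambda.min), 1,200 data sets per cell with one 80/20 split each (same expectation as the mean of 200 splits). True R² is taken from 1,000 new patients per fit. Pooled R² sums squared errors and divides once by the summed squared errors of the training mean.

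| Population R² | n | Mean per-split R² | Pooled R² | True R² of fitted model |
|---|---|---|---|---|
| 0 | 30 | -0.403 | -0.025 | -0.066 |
| 0 | 60 | -0.188 | -0.043 | -0.060 |
| 0 | 140 | -0.061 | -0.010 | -0.022 |
| 0.3 | 60 | -0.002 | 0.151 | 0.125 |
| 0.3 | 140 | 0.167 | 0.217 | 0.204 |
| 0.5 | 30 | -0.113 | 0.220 | 0.192 |
| 0.5 | 140 | 0.353 | 0.400 | 0.393 |

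With lambda.1se the no-signal per-split values are -0.43, -0.14 and -0.05 at n = 30, 60 and 140, in line with the closed form. A second simulation with 20 predictors gave -0.58, -0.20 and -0.07 without signal. With signal at n = 60 it gave -0.07 per split against +0.08 pooled and a true 0.07. Pooled values sit slightly above the true ones because their baseline is the training mean, which itself costs about 1/n_tr.

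**Effect on I1.** With no signal (lambda.min), going from n = 30 to n = 60 raises the per-split score by 0.403 - 0.188 = 0.215, while true performance rises by 0.066 - 0.060 = 0.006. From n = 60 to n = 140 the rises are 0.127 and 0.038.

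**Other statistics.**
- Mean correlation with no signal stays between -0.02 and +0.01. With signal (population R² 0.5) it is 0.515 against a true 0.542 at n = 30, and 0.633 against 0.639 at n = 140. At m = 2 a single correlation is always +1 or -1.
- Mean per-split RMSE for the training mean is 0.9792σ at n = 30 against √(1 + 1/24) = 1.0206σ, about 4% low. It is 0.9896 against 1.0104 at n = 60 (2% low) and 0.9955 against 1.0045 at n = 140 (1% low).
- Mean squared error shows no dependence on test-set size.

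**The case against.** The strongest reply is that the SAP never chooses R². It speaks only of relevant statistics, and the unseen table template may list a measure, such as mean squared error, for which nothing goes wrong. This stands: the point is conditional on the statistic.

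A reader might infer that the I1 curve rises with nothing to learn whatever is plotted. The calculations do not support that. Mean correlation stays flat at about 0. Mean RMSE drifts by about 2% towards looking worse (0.979σ to 0.996σ from n = 30 to 140). R² defined as squared correlation would fall, since its no-signal mean is 1/(m-1): 0.20 at m = 6 and 0.04 at m = 28. Even for R² about the test-set mean, part of the rise is genuine, because overfitting declines as n grows.

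A reader might also infer that clearly useful models will routinely be hidden. Signs flip mainly when about 40 or fewer patients are eligible or the signal is weak. Some low scores are deserved: with 20 predictors, population R² 0.3 and n = 30, the pooled score is itself -0.01. With everyone eligible at 140, the gap does not change the sign.

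The small test sets are partly assumed. SAP 4.2 plans to group drugs into a few classes, and if a treatment in A3 means a class, n_t is larger. The ceilings of 12 and 28 hold regardless.

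Finally, a spurious rise cannot push enrolment above plan, because protocol 4.2.3 allows only confirmation or reduction. It can only cost a reduction that the data might have justified.

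**Conclusion.** The point holds as a conditional weakness with a nearly free remedy. SAP 5.3 does state a rule, which is to score each test set and average, and it leaves the statistic open. Under R² about the test-set mean, the bias with no signal is modest if every completer is eligible (about -0.14 at the interim and -0.05 at the end). It becomes large when eligibility falls to 30 patients (-0.42), and the average is meaningless at three or fewer test patients. Comparisons across treatments and the slope of the I1 curve would then partly reflect sample size alone. Under correlation or RMSE the effect is small, apart from the very smallest test sets. Under mean squared or absolute error there is none.

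The documents do not support saying that the plan has adopted a biased measure, or that the interim will be misled whatever is reported. The sizes rest on normal outcomes, assumed numbers of predictors and signal strengths, and an unknown number of eligible patients per treatment. The change should be made; confidence is medium because of the unnamed statistic.

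**What to change.** In SAP 5.3 keep the ridge model and the 200 splits, and replace the sentence on average performance and unspecified statistics with two named quantities per treatment:

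1. Pooled RMSE: the square root of the mean squared error over all test predictions from all splits.
2. Predictive R² = 1 - (summed squared error of the model) / (summed squared error of the training-set mean on the same test patients), with both sums taken over all splits before dividing.

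State that R², correlation and RMSE are not averaged split by split. In 5.4.1 and Figure 7, use quantity 2 for the learning curve. If preferred, the 200 fits can be arranged as 40 repeats of five-fold cross-validation (40 × 5 = 200), so that each patient is tested equally often.

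The cost is a few sentences in the SAP and a few lines of code, with the same number of fits and no new data. The small downside is that the spread across single splits is no longer the headline summary; it can still be shown for squared error.
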